1.1 Background of Trial Plan

Acute myeloid leukemia (AML) is a malignant disease derived from myeloid hematopoietic cells. In AML, unregulated proliferation of leukemia cells is associated with inhibition of normal hematopoiesis. AML is a life-threatening disease with various symptoms such as infection, anemia, hemorrhage due to thrombocytopenia, and organ disorders. Although AML occurs in people of all ages, it is known to be more prevalent among the elderly, and the median age of onset is reported to be 62 years in Japan.¹ Treatment of AML is based on the concept of total cell kill. Normally, after complete remission (CR) is achieved by remission induction therapy to reduce leukemia cell count to below 10^9 cells, consolidation therapy is performed to further reduce the number of residual leukemia cells to near zero.² However, it is not rare for patients, especially elderly patients, to experience relapse due to proliferation of residual leukemia cells after CR. The prognosis for AML becomes worse as age increases. There are many reasons for this. For one, the deterioration in organ functions (including bone marrow, liver, cardiorespiratory and renal functions) in the elderly constitutes a barrier to adequate AML therapy. Also, AML in elderly patients more frequently arises from antecedent hematologic disorders such as myelodysplastic syndrome (MDS), which is always associated with a worse outcome. Moreover, elderly AML patients have a higher incidence of poor-risk cytogenetics, which is associated with poor outcome. In an investigation involving elderly AML patients (aged 50 to 70 years) not receiving allogeneic hematopoietic cell transplantation, even for those patients who achieved CR, the 3-year relapse-free survival (RFS) was as low as 29% and many patients experienced relapse.³ When treating elderly patients with antitumor drugs, it may be necessary to reduce the dose. There are a considerable number of limitations and much debate regarding therapeutic regimens in elderly patients with leukemia. Therefore, a new therapy is needed to prevent relapse of AML, and extend survival of elderly patients with AML.

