3.4 Target Number of Patients

The planned number of patients is 120 in total (60 patients in the OCV-501 arm and 60 patients in placebo arm).

4 Investigational Medicinal Products

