7.1.2.2 Subject Information

At the time of obtaining informed consent or at the screening examination, the following subject information will be recorded in the medical records (if necessary) and the CRF.

- Date of informed consent acquisition
- Subject number
- Subject's background information:
 - Sex
 - Date of birth (year, month, day),
 - Country where the trial was conducted
 - Race
- Information of AML and other malignancies:
 - Diagnosis of AML (WHO classification) and date of diagnosis
 - Caryotype or cytogenetic abnormalities of AML at the diagnosis
 - Existence of extranodullary disease
 - Percentage of leukemic blast (bone marrow blast) at the diagnosis
 - Regimen of induction therapy (name of drug, dose) and date of start.
 - Number of courses until CR is achieved
 - Date of CR by induction therapy
 - Regimen of consolidation therapy (name of drug, dose) and date of start.
 - Number of courses of consolidation therapy
 - Last date of administration of consolidation therapy
 - Maximum WT1 mRNA level and date of sample collection at AML diagnosis or at the time of induction therapy or consolidation therapy (if possible).
 - Diagnosis of malignant tumor other than AML and date of diagnosis and date of cure

- Treatment of malignant tumor other than AML
- Medical history and concomitant disease:
 - Medically significant medical history and date of diagnosis
 - Diagnosis of concomitant disease at the time of obtaining informed consent, and date of diagnosis

7.1.2.3 Allocation of Investigational Medicinal Products to Subjects at Enrollment (Before Week 1 IMP Administration)

From the results of the screening examination, the investigator or subinvestigator will verify that the subject meets the inclusion criteria and does not fall under any of the exclusion criteria, and each subject will be registered in either the IVRS or the IWRS and assigned a treatment allocation code. Date of the enrollment will be recorded in the medical records and CRF.

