3.1.1 Screening Period

The eligible patients will be randomly assigned to one of the following treatment arms at a ratio of 1:1

- OCV-501 arm: 3 mg of OCV-501 (0.4 mL)
- Placebo arm: Placebo (0.4 mL)

The patients will be assigned to either treatment arm via the interactive voice response services (IVRS) or the interactive web response services (IWRS).

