4.5 Demographic and Other Baseline Characteristics

1) Definition:

Demographic:

Age, sex, height, body weight (at screen), race, trial country/region

Age will be divided into 3 groups (60 to 64 years, 65 to 70 years, ≥ 71 years).

Underlying diseases, induction/consolidation therapy and other baseline factors

Diagnosis of AML (WHO classification), duration from the last dose of consolidation therapy to randomization, duration from diagnosis of AML to randomization, regimen of number and therapy (induction, consolidation), WT1 mRNA level at Day 1, unfavorable karyotype abnormality (abn(3q)/inv(3)/t(3;3) or -5/del(5q) or -7/del(7q) or t(6;9)), cytogenetic abnormality (FLT3-ITD mutation)

WT1 mRNA level (copy/ugRNA) will be divided into 4 categories (<50, 50-199, 200<= and Unknown).

Prior and concomitant drugs/treatments

Prior and concomitant medications will be classified by Anatomic Therapeutic Chemical Classification 2 (ATC2) and generic (preferred) name using World Health Organization Drug Dictionary (WHO-DD).

The start or stop dates of administration of drugs/treatments other than IMP will be compared to the date of first IMP administration to classify them as either prior or concomitant drugs/treatments.

Table 4.5-1 Prior and Concomitant Drugs/Treatments	
Prior	Stop date of drug/treatment \leq First IMP administration date
Concomitant	Stop date of drug/treatment $>$ First IMP administration date

Concomitant drugs/treatments starting after the completion/withdrawal date will be listed but will not be classified or summarized.

Medical history and Concomitant disease

Medical history and concomitant disease are coded using Medical Dictionary for Regulatory Activities (MedDRA version 20.1). If the condition is not continuing at the

time of informed consent, it is considered as medical history. If the condition is continuing, then it is concomitant disease.

2) Analysis Set:

FAS, PPS, SS, IRS

3) Analysis Method:

Frequency counts and percentage or descriptive statistics for each variable will be calculated according to the nature of the data (continuous or discrete) by treatment arm and overall. For WT1 mRNA level, the measurement “<50” will be translated into 49 when calculating descriptive statistics.

The following summaries will be generated.

- A summary of demographic variables at baseline by treatment arm and over all
- A summary of other baseline characteristics by treatment arm and overall

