 - In the model of Cox analysis, treatments effect will be adjusted with covariates (Age, Country/Region and WT1 mRNA level at Day 1). The model with covariates (WT1 mRNA only) or model without covariates will be also analyzed. In these models, age will be categorized into 3 groups (60 to 64 years, 65 to 70 years, ≥ 71 years), Country/Region into 2 groups (Japan, Republic of Korea+Taiwan), WT1 mRNA into 4 groups (<50, 50-199, 200<= and Unknown).
 - BRESLOW method will be used for ties.
 - Proportionality assumption in Cox proportional hazard model will be assessed using 2 methods:
 - 1) SAS PHREG procedure ASSESS PH option will be used for checking proportional hazard assumption.
 - 2) Look at the log-minus-log survival plots graphically. If the graph results in parallel lines then the proportionality assumption is satisfied.
- HR and its 95% CI at every 3 months interval will be calculated by adding a time varying covariate to Cox Proportional Hazards model as an alternative analysis if the proportionality assumption fails. The model will be as follows:

$$\lambda(t;X) = \lambda_0(t) \exp(\beta_1 \text{trt} * \text{period}_1 + \beta_2 \text{trt} * \text{period}_2 + \dots)$$

where $\lambda_0(t)$ is the baseline hazard function,

trt is the treatment arm(1= OCV-501 and 0= Placebo) and

$$period_1 = \begin{cases} 1 & \text{if } 0 \leq DFS \text{ time} < 3 \text{ Months} \\ 0 & \text{otherwise} \end{cases}$$

$$period_2 = \begin{cases} 1 & \text{if } 3 \leq DFS \text{ time} < 6 \text{ Months} \\ 0 & \text{otherwise} \end{cases}$$

...

So HR (OCV-501 vs. Placebo) for each period will be calculated as follows:

$$\lambda(\text{OCV-501}|\text{period}_k) = \lambda_0(t)\exp(\beta_k)$$

$$\lambda(\text{Placebo}|\text{period}_k) = \lambda_0(t)$$

$$\text{HR}(\text{OCV-501 vs. placebo}|\text{period}_k) = \lambda_0(t)\exp(\beta_k) / \lambda_0(t) = \exp(\beta_k)$$

$$95\% \text{ CI} : [\exp(\beta_k - 1.96 * \sqrt{\text{Var}(\beta_k)}), \exp(\beta_k + 1.96 * \sqrt{\text{Var}(\beta_k)})]$$

- For exploratory purposes, the incidence rate over the entire follow-up period will be calculated using the person-year method by treatment arm as follows.

- 1) Calculate the number of events and person-year at risk by treatment arm.
- 2) Calculate the incidence rates and its corresponding 95% CI by treatment arm. (1 year is calculated as 365.25 days)

$$\text{Rate} = \frac{\text{Number of events}}{\text{Person - year}}$$

95% CI:

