4.12 Determination of Sample Size

The number of AML patients is not very high, and is estimated to be approximately 7000 in Japan⁷. From the fact that in the previous clinical trial (JALSG GML200) in elderly AML patients, it has been forecast that the possible enrollment in Japan is to be at most 70 in one year. Also, from the preliminary trial feasibility survey, it is known that around 50 subjects could be recruited in one year in the Republic of Korea and Taiwan. Through a global trial in Japan, the Republic of Korea and Taiwan, it is considered possible to enroll 120 subjects in one year to assess the efficacy of OCV-501.

Within the limitation of the past experiences with regard to IMP administration, the target sample size will be considered with reference to following publications.^{5,6,7,9} With reference to disease-free survival which has been reported from trials in AML patients 60 years or older who have received the consolidation therapy followed by maintenance therapy, the 2-year DFS rate of placebo arm has been estimated to be around 20%.^{5,6,7}

On the other hand, considering the so-called graft-versus-leukemia (GVL) effect associated with a lower relapse risk after the allogeneic hematopoietic stem cell transplantation, OCV-501 is basically expected to have the same benefits. With reference to the findings of Kurosawa et al,⁹ which have reported a 30% higher 2 or 3-year DFS in elderly AML subjects who have received the allogeneic hematopoietic stem cell transplantation compared with those without transplantation, OCV-501 is expected to have a 15% - 20% higher 2-year DFS. Under the assumption of exponential distribution of DFS time, the hazard ratio (placebo vs. OCV-501) has been set to 0.57 - 0.65, and with a two-sided log-rank test at the 5% significance level, 60 or more subjects in each treatment group can achieve a power of 53% - 75% or more to detect the difference between placebo and OCV-501 groups.

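### The supportive adjusted Cox model for DFS and OS leaves out unfavourable karyotype, so no planned analysis accounts for a chance imbalance in it

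*SAP*

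**What the plan says.** - SAP 4.7.1.1: "treatments effect will be adjusted with covariates (Age, Country/Region and WT1 mRNA level at Day 1". Age has three groups, country/region two and WT1 mRNA four, one of them for unknown values. Two further Cox models are planned, one with WT1 mRNA alone and one with no covariates. SAP 4.7.2.1 applies the same analyses to OS.
- SAP 4.5 derives "unfavorable karyotype abnormality" from an explicit list of abnormalities, for descriptive summary.
- Protocol 7.1.2.2 collects "Caryotype or cytogenetic abnormalities of AML at the diagnosis".
- Protocol 1.1 states that "elderly AML patients have a higher incidence of poor-risk cytogenetics, which is associated with poor outcome".
- Protocol 6.3 stratifies randomization by country/region and age. SAP 4.11 uses the same two factors for subgroups. Karyotype is in neither.
- The primary test is an unadjusted log-rank test (SAP 4.7.1.1). Protocol 11.3.1.1 lists the covariate-adjusted Cox model, there with country and age only, among the exploratory methods. SAP 4.13 says the adjusted models are there to examine how covariates influence the result.

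**The concern.** The SAP extended the protocol's adjusted model by adding Day 1 WT1 mRNA, but left out the cytogenetic factor that the protocol's own background ties to outcome, and gives no reason. The data will be in hand, the variable is already defined, and missing values have a precedent in the unknown class for WT1 mRNA.

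With 60 patients per arm and no stratification on karyotype, the arms may differ by chance. The baseline table would show this but would not correct for it. If no karyotype-adjusted estimate has been prespecified, any such estimate produced after unblinding will be a choice made with the results in view. A prognostic covariate left out of the model also costs some precision, in a trial whose stated power is only 53–75%.

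**Working it through.** **Inputs from the documents.** Sample size "120 in total (60 patients in the OCV-501 arm and 60 patients in placebo arm" (Protocol 3.4). Allocation: "The eligible patients will be randomly assigned to one of the following treatment arms at a ratio of 1:1" (SAP 3.1.1). Test: "with a two-sided log-rank test at the 5% significance level" (SAP 4.12). Control rate: "the 2-year DFS rate of placebo arm has been estimated to be around 20" per cent (SAP 4.12). OCV-501 is expected to be 15–20 points higher, so 35–40%.

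**Inputs not in the documents (assumed).** Prevalence of unfavourable karyotype q = 10–30%; karyotype hazard ratio g = 1.5–3.

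**1. The plan's own power.** With exponential DFS, HR (OCV-501 to placebo) = ln(p_OCV)/ln(p_placebo).
- ln 0.35/ln 0.20 = 0.652. Events by 2 years: 60(0.80) + 60(0.65) = 87.
- ln 0.40/ln 0.20 = 0.569. Events: 60(0.80) + 60(0.60) = 84.

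Schoenfeld power = Φ(½√D·|ln HR| − 1.96):
- Φ(1.993 − 1.96) = 51.3%
- Φ(2.581 − 1.96) = 73.3%

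The stated 53–75% is reproduced to within 2 points.

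**2. How often the arms differ.** The SD of the between-arm difference in prevalence is √(2q(1−q)/60). A gap of at least 10 points means at least 6 patients; its probability is exact, from two independent binomials.

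| q | SD (points) | 95% limit (points) | P(gap ≥ 10 points) |
|---|---|---|---|
| 10% | 5.5 | ±10.7 | 9% |
| 20% | 7.3 | ±14.3 | 21% |
| 30% | 8.4 | ±16.4 | 27% |

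**3. How far a gap moves the unadjusted hazard ratio.** To first order the factor is g^δ for a gap δ.
- At δ = 0.10: 1.5^0.10 = 1.04, 2^0.10 = 1.07, 3^0.10 = 1.12.
- At the 95% limits: from 1.04 (q = 10%, g = 1.5) to 1.20 (q = 30%, g = 3).

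**4. What adding karyotype to the SAP's model gains.** The relevant comparison keeps age, country and WT1 mRNA in both models and adds karyotype with an unknown class. It was simulated with true HR 0.57, 10% unknown, and assumed age and WT1 effects, in two separate runs of about 1,000 and 500 replicates per setting.

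| q, g | Gain in power (points) |
|---|---|
| 10%, 1.5 | about 0 to 1 |
| 20%, 2 | about 3 |
| 30%, 3 | about 7 to 10 |

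With 500 replicates, the Monte Carlo standard error of a power near 70% is √(0.7 × 0.3/500), about 2 points.

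**5. Size of the model.** Treatment 1 + age 2 + country/region 1 + WT1 mRNA 3 = 7 parameters. Adding karyotype yes and unknown makes 9. Events per parameter fall from 84/7 = 12.0 to 84/9 = 9.3, or from 87/7 = 12.4 to 87/9 = 9.7. This assumes that all 120 patients are followed for 2 years.

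**6. Type I error.** In simulations at HR 1 with no other covariates (1,500 runs per setting), rejection was 4.5–5.3% without karyotype and 4.5–5.9% with it.

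**The case against.** The strongest reply is that this touches nothing decisive. The primary inference is the log-rank test, the adjusted model is exploratory or supportive, and covariate choice is a judgement. The chosen set covers both stratification factors plus Day 1 WT1 mRNA, a residual-disease marker that may carry some of the same information as karyotype. Chance imbalance is already part of what the confidence interval expresses: with 84 events the unadjusted 95% interval spans a factor of exp(1.96 × 2/√84) = 1.53 either way, so a shift of 4–12% from a 10-point gap lies well inside it. All of this stands and limits the weight of the point.

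The assumptions are also open. Protocol 1.1 speaks of elderly AML in general. The trial enrols patients in first remission within two induction courses who have completed consolidation, and SAP 4.5 uses a short list of abnormalities. Prevalence could be low and the gain negligible, so the range has to include about zero.

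FLT3-ITD is derived next to karyotype and is also left out of the models. The protocol background singles out cytogenetics, which is a reason to take karyotype first, but it does not settle the question for FLT3-ITD.

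Two stronger readings are tempting. A reader might infer that omitting karyotype biases the treatment hazard ratio toward 1. In simulations without other covariates, a conditional HR of 0.57 did correspond to a large-sample unadjusted HR of 0.572–0.606, up to about 6% higher. That is non-collapsibility: under randomization the unadjusted ratio correctly estimates a marginal effect. A reader might also compare no covariates with karyotype alone, where power rises from 62.5% to 74.1% at q = 30% and g = 3. The SAP's adjusted model already holds three covariates, so that is not the change at issue.

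The case for adding karyotype survives in reduced form. The baseline table can reveal an imbalance, but no planned estimate answers it.

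**Conclusion.** The point holds as a modest improvement to a supportive analysis. A factor that is collected, already derived and described by the protocol as prognostic enters neither the randomization nor any efficacy model. Under the assumed ranges (prevalence 10–30%, karyotype HR 1.5–3), a gap of at least 10 points occurs in about 9–27% of trials. Including karyotype in the SAP's adjusted model gains roughly 0 to 10 points of power at a true HR of 0.57, with the upper end only for a common and strong factor. The simulated gain also rests on assumed age and WT1 effects and on a 10% unknown rate.

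A reader might infer that the primary result is compromised. The documents do not support that: the log-rank test uses no covariates, and its type I error does not depend on karyotype being modelled. What is missing is precision in the adjusted estimate and a prespecified response if karyotype turns out unbalanced.

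**What to change.** Before unblinding, add unfavourable karyotype (yes/no/unknown, as defined in SAP 4.5) to the covariate-adjusted Cox model in SAP 4.7.1.1, and so to OS through 4.7.2.1. Keep the unadjusted and WT1-only models as planned, and record the addition in SAP 4.13. If about 9.5 DFS events per parameter is judged too thin, particularly in the smaller per-protocol set, leave the planned adjusted model as it is and prespecify the karyotype version as a sensitivity analysis.

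The cost is one line in the SAP, two more parameters (7 to 9) and an unknown class that may be sparse. No new data are needed.

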4.7.1 Primary Efficacy Endpoints

4.7.1.1 Disease-free Survival

1) Definition:

- Observation period: For each subject, the time from randomization to the DFS-cutoff date. The DFS-cutoff date was set as the completion/discontinuation date of each subject.
- DFS: The time from randomization until relapse or death from any cause, whichever comes first by the DFS-cutoff date.
- Event: Relapse or death from any cause by the DFS-cutoff date.
- Censoring:
 - If an event has not been observed by the DFS-cutoff date, then the last confirmed non-relapse date will be used as the censoring date.
 - For subjects who have withdrawn from this trial before the completion date for reasons other than relapses or deaths, if non-relapse has been confirmed on the withdrawal date, then the withdrawal date will be used as the censoring date. Otherwise, the last confirmed non-relapse date will be used as the censoring date.

2) Analysis Set:

FAS (primary), PPS

For the judgment of relapse by the central pathological review committee, DFS will be evaluated in the FAS and PPS as primary analysis.

For the judgment of relapse by trial site, DFS will only be evaluated in the FAS as secondary analysis.

3) Analysis Method:

- Primary test for comparison between OCV-501 and Placebo will be conducted by Log-rank test. For exploratory purposes, the Harrington-Fleming (HF) test will be performed by applying the weight $1 - \hat{S}(t)$, where $\hat{S}(t)$ is the product-limit estimates of survival functions.
- Kaplan-Meier estimate of survivor function $\hat{S}(t)$ and curve

$$\hat{S}(t) = \Pr(\text{Survive beyond } t)$$
$$= \prod_{j: t_j < t} \left(\frac{n_j - y_j}{n_j} \right)$$

where t_j is the j -th event time, n_j is the number of patients at risk and y_j is the number of events.

The Kaplan-Meier curve plots the estimated survival function $\hat{S}(t)$ vs. time separately for each treatment arm.

- The 2-year survival rate and median survival time will be calculated. The 95% CI of the 2-year survival rate will be calculated using Greenwood formula.
- Hazard ratio (HR) and its 95% CI will be calculated from the Cox proportional hazards model.

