4.7.2 Secondary Efficacy Endpoints

4.7.2.1 Overall Survival

1) Definition:

- Observation period: For all subjects, the time from randomization to OS-cutoff date. The OS-cutoff date was set as the date after 728 days (2 years) from the day that the last subject started IMP administration without consideration of withdrawal by the OS-cutoff date.

- Definition: The time from randomization until death from any cause by the OS-cutoff date.
- Event: Death from any cause by the OS-cutoff date.
- Censoring: If an event has not been observed by the OS-cutoff date, then the last confirmed survival date will be used as the censoring date.

2) Analysis Set:

FAS, PPS

3) Analysis Method:

The same analysis will be conducted as for DFS.

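### SAP 4.7.1.1 defines the 3-month period indicators by each subject's own DFS time instead of running time t; coded literally, the model shows false early harm, so the notation needs a minor correction.

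*SAP*

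**What the plan says.** SAP 4.7.1.1 plans interval-specific hazard ratios: "HR and its 95% CI at every 3 months interval will be calculated by adding a time varying covariate to Cox Proportional Hazards model". They are to be used "as an alternative analysis if the proportionality assumption fails". The hazard is written as a function of t and X, with one treatment-by-period coefficient per interval, and exp(beta_k) is reported as the hazard ratio for period k.

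The indicators are then displayed. The first equals 1 when *DFS time* lies from 0 to under 3 months, the second when it lies from 3 to under 6 months, and the list continues with dots. No last interval is given.

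Earlier in the same section, DFS is defined as the outcome: "DFS: The time from randomization until relapse or death from any cause, whichever comes first by the DFS-cutoff date". SAP 4.12 uses the phrase in the same sense when it assumes an exponential distribution for DFS time.

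OS takes over the method: "The same analysis will be conducted as for DFS". Section 4.7.3.1 does the same for DFS until OS cutoff.

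**The concern.** A time-varying effect needs an indicator that depends on where the clock stands, the same for everyone still at risk. The printed indicator depends on when that particular subject will fail or be censored. If it is derived once per subject, the OCV-501 arm is sorted by its own outcome while every placebo subject carries zeros. The first coefficient then compares OCV-501 subjects already known to leave within 3 months with placebo subjects of every outcome. It will be large whatever the drug does.

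At stake is the estimate that the SAP would turn to if proportionality fails, for DFS, OS and DFS until OS cutoff. The SAP calculates person-year incidence rates over the whole follow-up only, so no planned interval-specific rate would expose a wrong 3-month ratio.

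**Working it through.** **1. The wording side by side**

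- Pointing to running time: the lead-in sentence (a covariate that varies over time), the hazard written in t, a hazard ratio stated per period, and SAP 4.13, which presents the 3-month analysis as the alternative to a Cox model over the whole period.
- Pointing to the subject's outcome: the displayed condition itself, since *DFS time* is the outcome in 4.7.1.1 and in 4.12. The symbol t was available; it is used in the Kaplan-Meier formula and in the baseline hazard of this same model.

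**2. Inputs**

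- 60 per arm, 20% 2-year DFS on placebo, exponential DFS (SAP 4.12).
- Two years of DFS observation (protocol 3.2), so 24/3 = 8 intervals.
- Ties: "BRESLOW method will be used for ties" (SAP 4.7.1.1).
- Sensitivity range for 2-year DFS: 10% to 30% (protocol 3.2).
- Assumption: no withdrawal in the base case; 15% withdrawal as a variant.

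**3. The plan's own figures**

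The 3-month model has no stated figure. The planning figures behind the inputs do reproduce:

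- Hazard ratios: ln(0.35)/ln(0.20) = 0.652 and ln(0.40)/ln(0.20) = 0.569, matching the stated 0.65 and 0.57.
- Expected events: 60 x 0.80 + 60 x 0.65 = 87, and 60 x 0.80 + 60 x 0.60 = 84.
- Schoenfeld power, two-sided 5%: 51.3% and 73.3%, within 2 points of the stated 53% and 75%.

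**4. Why the literal coding fails**

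The monthly hazard is -ln(0.20)/24 = 0.0671. The chance of an event before month 3 is 1 - exp(-3 x 0.0671) = 0.182. With no drug effect, about 60 x 0.182 = 10.9 OCV-501 subjects get the first label, and without withdrawal all of them have an event by month 3. Among placebo subjects, who are not sorted, 18% do. The model reports that contrast as a treatment effect.

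**5. Simulation with no treatment effect, 2-year DFS 20% in both arms (median hazard ratios)**

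| Coding | 0-3 | 3-6 | 6-9 | 9-12 | 12-15 | 15-18 | 18-21 | 21-24 |
|---|---|---|---|---|---|---|---|---|
| Fixed label, completers in last interval | 38 | 7.6 | 3.3 | 1.9 | 1.3 | 0.92 | 0.71 | 0.09 |
| Fixed label, completers all zero | 50 | 9.9 | 4.3 | 2.5 | 1.7 | 1.3 | 1.0 | 0.84 |
| Evaluated at risk-set time t | 0.99 | 0.99 | 1.02 | 0.92 | 1.02 | 1.00 | 0.92 | 0.98 |

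- First row: separate runs put the first interval between 37.7 and 39.5 and the second at 7.5 or 7.6. The 95% CI lay wholly above 1 in 100%, 99.7% and 84% of trials in the first three intervals.
- Third row: the CI excluded 1 in at most about 6% of trials in any interval.
- With 15% withdrawal, the first-row coding gives 34, 6.9 and 2.9 in the first three intervals and 0.10 in the last.
- With a true hazard ratio of 0.57, evaluation at t gives 0.55 to 0.63 throughout. The first-row coding gives 27, 6.5, 3.1, 1.9, 1.3, 0.95, 0.73 and 0.05, almost the same picture as with no effect.

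**6. Sensitivity to the DFS rate and to the placing of completers (400 trials each)**

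| 2-year DFS, both arms | First interval: completers in last / all zero | Last interval: completers in last / all zero |
|---|---|---|
| 10% | 24 / 26 | 0.09 / 0.50 |
| 20% | 40 / 50 | 0.09 / 0.84 |
| 30% | 64 / 85 | 0.10 / 1.24 |

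Early harm appears in every case. With completers coded zero, the last-interval CI lies below 1 in 0% to 3% of trials; with completers in the last interval, it does so in essentially all.

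The schedule does not settle which applies. The Week 103 window is Day 710-720 and completion follows 11-17 days later, so Day 710 + 11 = 721 to 720 + 17 = 737, counted from first dose. Two years is 2 x 365.25 = 730.5 days, inside that range.

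**The case against.** The strongest reply is that nobody would run the literal version. The governing sentence asks for a time-varying covariate, the hazard is a function of t, the ratio is stated per period, and 4.13 contrasts 3-month intervals with the whole period. The software is SAS, and the SAP names the procedure: "SAS PHREG procedure ASSESS PH option will be used for checking proportional hazard assumption". In PHREG programming statements the response variable takes the risk-set time, so even the printed condition gives the right answer there. The error needs a programmer to build the indicators beforehand as fixed variables. SAP 4.1 also requires outputs to be checked independently, and a first-interval ratio near 38 would look odd beside overlapping Kaplan-Meier curves.

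Most of this stands, and it rules out the reading that the SAP prescribes a biased analysis. It does not clear the notation. The SAP does not say where the indicators are to be coded, and a check against the written formula may pass a program that follows it exactly.

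A reader might also infer that the artefact imitates a delayed vaccine effect, with early harm followed by strong late benefit. The documents do not support that as a general result. The last-interval ratio near 0.1 arises only if event-free completers are placed in the last interval, and the SAP gives no rule for them. Only the early-harm half is stable, and that half would not flatter the product.

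**Conclusion.** This is a real inconsistency and a minor correction. The displayed indicators contradict the sentence that introduces them. Applied literally as subject-level variables, they give median hazard ratios of about 38, 7.5, 3.3 and 1.9 in the first four intervals when the true value is 1. Evaluated at t, the ratios are about 1. The size rests on 60 per arm, exponential DFS, 20% 2-year DFS and two years of follow-up. The direction of the early error held at 10% and 30% and with 15% withdrawal.

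It should not be read as a threat to the main result. The log-rank test, the Kaplan-Meier estimates and the overall Cox hazard ratio do not use these indicators. The analysis runs only if proportionality fails, and protocol 11.3.1.1 lists the 3-month ratios as exploratory. OS and DFS until OS cutoff inherit the wording but were not simulated. Their follow-up runs to a common cutoff and so exceeds two years for earlier entrants, which makes an explicit last interval more necessary there.

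**What to change.** In SAP 4.7.1.1:

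- Replace *DFS time* by t in every indicator: period_k(t) = 1 if 3(k-1) <= t < 3k months since randomisation, and 0 otherwise.
- Add one sentence: the indicators are evaluated at each risk-set time, using (start, stop) records or PHREG programming statements, and are not derived as fixed variables in the analysis dataset.
- State the upper bound of the last interval, so that it is clear where follow-up at or beyond 24 months belongs.

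Apply the same wording to OS (4.7.2.1) and DFS until OS cutoff (4.7.3.1), with t as time since randomisation in each and a last interval suited to the longer follow-up.

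The cost is one symbol and a sentence or two, made before unblinding. Data collection, sample size and the primary test are unchanged.
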